Bidlingmaier et al conducted the most comprehensive literature review of the safety and efficacy of LMWH in children up to 18 years old.⁴³ They reviewed 8 studies in which LMWH was used as prophylaxis against DVT. Of 305 children analyzed, only 7 (2.3%) developed DVT and 7 (2.3%) had clinically relevant bleeding while on the drug.

Recently, co-I [name] studied enoxaparin as prophylaxis against DVT that was not associated with a CVC in critically ill adolescents as part of a quality improvement initiative.⁶ Enoxaparin was given subcutaneously every 12 hours at 0.5 mg/kg (maximum of 30 mg). No DVT that was not associated with a CVC and no clinically relevant bleeding occurred in 90 adolescents in the study

STATEMENT OF PURPOSE/OBJECTIVES

Aim 1: To obtain preliminary evidence on the effect of early prophylaxis on the incidence of CADVT in critically ill children.

Hypothesis – Among critically ill children, prophylaxis administered <24 hours after insertion of the CVC decreases the incidence of ultrasound-diagnosed CADVT compared with no prophylaxis. The natural history of CADVT in children suggest that prophylaxis needs to be administered <24 hours after the insertion of the CVC to maximize the likelihood of preventing CADVT.^{18, 19, 21}

Aim 2: To evaluate the effect of an anti-Xa activity-directed prophylactic strategy on thrombin generation in critically ill children

Hypothesis –Among critically ill children, standard prophylactic dose of enoxaparin adjusted by anti-Xa activity reduces thrombin generation to <700 nM·min, as measured by ETP. In non-critically ill adults, prophylactic dose of enoxaparin proven to prevent DVT reduces ETP to <700 nM·min.^{15, 26}

PHARMACEUTICAL AND THERAPEUTIC BACKGROUND

Product Description

Enoxaparin is a LMWH produced from UFH that exerts its anticoagulant effects by binding to and inducing a conformational change in antithrombin to accelerate the inactivation of factor Xa and thrombin.^{12, 44} Enoxaparin is the most commonly used thromboprophylactic agent in adults and children. It is equipotent with other LMWH. In contrast to UFH, enoxaparin has significantly greater inhibitory activity against factor Xa and has lower risk of bleeding and HIT. It has good bioavailability with predictable pharmacokinetics requiring less monitoring compared with UFH.

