The frequency of clinically relevant bleeding in critically ill children in the absence of anticoagulation is 0%-3% while that of children on prophylaxis with LMWH is 2.3%.^{43, 54-57} If ≥ 5 clinically relevant bleeding events (100 children \times 5.3% \approx 5 events) occur, the

safety monitor will notify the chair of the data DSMB. The DSMB chair may convene a meeting or teleconference of the DSMB to consider the concerns and plan appropriate action, including temporarily putting the trial on hold. Because of the difficulty in determining the relationship between bleeding events and enoxaparin in critically ill children, all bleeding events will be conservatively attributed to the drug unless the child has not received a dose for ≥ 30 hours, which corresponds to 5 half-lives of the drug.

CORRELATIVE SAMPLES

Blood

Blood for correlative studies will be drawn from the CVC into two 2.7 mL citrated tubes at the following four time points

1. Draw 1 (D1): <24 hours after insertion of CVC (and before enoxaparin is administered for subjects in the control arm)
2. Draw 2 (D2): 24±6 hours after D1 (or together with the blood draw for the anti-Xa activity for subjects in the treatment arm)
3. Draw 3 (D3): 4 days after insertion of CVC (if the child is still in the study at that time)
4. Draw 4 (D4): At the end of the study period

Blood will be processed locally using standard procedures for obtaining platelet-poor plasma. It will then be frozen at -70°C.⁵⁸ All specimens will be shipped to Yale for banking and will be analyzed every 6 months.

At any one of the time points specified above, additional blood will be drawn into one 0.5 mL EDTA tube for future genetic analysis. No processing is needed prior to freezing this sample.

Urine

At time points (D1-4) specified above for blood collection, 2-5 mL of urine will also be collected in urine collection tubes for correlative studies. No processing will be needed prior to freezing the urine locally at -70°C. Administration of enoxaparin should not be delayed if urine is not available before first dose of the drug is administered.

Please refer to laboratory manual for specific instructions on processing, storage and shipment of blood and urine samples to Central Laboratories for analyses and storage. Blinded personnel at each Central Laboratory will perform all assays in duplicate on platelet-poor plasma collected at all time points. Results will be averaged for analysis.

CORRELATIVE STUDIES

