We define clinically significant efficacy of prophylaxis as $\delta \geq 0.06$. The absolute proportion reduction ≥ 0.06 (i.e., relative risk reduction $\geq 33\%$, relative to 0.18) is considered clinically significant in prior pediatric RCTs of prophylaxis against CADVT and is consistent with that achieved in RCTs of prophylaxis in critically ill adults.^{5, 63} In our recent meta-analysis, we showed that the proportion of children with no enoxaparin prophylaxis who developed CADVT was $pS = 0.18$ (95% CI: 0.12-0.25).⁵ Based on the finding from this meta-analysis, we will use an informative prior of $pS \sim B(18,82)$. Because we know very little about pE , a non-informative prior of $pE \sim B(1,1)$ will be used. We will assess the robustness of our results via sensitivity analyses that are based on other choices for hyper-parameters α, β for $pE \sim B(\alpha,\beta)$ and $pS \sim B(\alpha,\beta)$ that may have implications for salient results.

The accepted threshold of posterior probability for not proceeding with a phase 3 trial after a phase 2 trial for success is >0.90 , while the threshold for not proceeding for futility is unique to each study.^{64, 65} If our results suggest that the posterior probability of $\delta \geq 0.06$ is less than 0.60, then we will not proceed with a phase 3 trial using the same dose of enoxaparin. We will determine whether a higher dose is appropriate from the results of Aim 2.

Subjects will be randomized 1:1 to the 2 treatment arms. An interim analysis of the binary outcome CADVT status consisting of the first 50 subjects enrolled will be performed to assess if the futility boundary has been crossed. Futility in the interim analysis will be defined as a predictive probability <0.10 for $\delta \geq 0.06$. The same primary analysis priors for pS and pE mentioned above will be used for the interim analysis. There will be no interim stopping or adaptation based on efficacy.

For Aim 2, we will calculate the posterior probability that the ETP with enoxaparin is <700 nM·min for difference of means of ETP at D2 after 100 subjects complete the trial. We chose D2 because anticoagulation should be achieved as soon as possible. We

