used an informative prior of ETP without enoxaparin $\sim N(1443, 356)$ from healthy children and a non-informative prior $\sim N(0, \infty)$ for ETP without enoxaparin due to lack of data in critically ill children.^{48,94} The posterior probability that ETP with enoxaparin < 700 nM·min is ≥ 0.60 will be used to decide on the dose for a phase 3 trial. For secondary analysis, we will analyze the primary outcome of ETP over time (D1-D4) using intent-to-treat principle and Bayesian linear mixed effects model with treatment arm as the main predictor of interest, adjusted for the stratifying variables of age and ICU. We will analyze the relationship of ETP with anti-Xa level using linear mixed effects model, then identify explanatory variables from the coagulation-related markers. From the clinical variables, we will identify those that are associated with achieving the target ETP and anti-Xa level using generalized estimating equations. Using a joint model of linear mixed effects model for ETP or anti-Xa level, and generalized linear model for CADVT or bleeding, we will examine the relationship of ETP and anti-Xa level with CADVT and clinically relevant bleeding. We will use SAS[®] v9.4, WinBUGS, or R packages to perform Bayesian modeling and data analysis.

DATA MANAGEMENT AND RECORD KEEPING

The investigators are required to prepare and maintain adequate and accurate case histories designed to record all observations and other data pertinent to the investigation on each individual treated in the investigation. Data that are derived from source documents and reported on the CRF must be consistent with the source documents or the discrepancies must be explained. OnCore will be the designated electronic data capture tool. All data should be entered onto OnCore within 1 week of study entry. AEs need to be entered within 72 hours and SAEs need to be entered within 24 hours of the site becoming aware of the event.

ADMINISTRATIVE AND REGULATORY

Multicenter Management and Coordination

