Data will be entered into OnCore. De-identified data will then be downloaded in Excel format for statistical analysis, which will be done on a HIPAA compatible, password protected encrypted laptop computer by biostatistician co-I [name] for use. All data entry will be performed by the local study site personnel. All source documentation will be retained at the local study site per local site regulations and monitored during regularly scheduled monitoring visits.

TRIAL FLOW CHART

Procedure	Screening Period	Treatment Period	End of Study CVC Removal
Parental permission/assent	X		
Review of eligibility criteria	X		
Randomization	X		
Medical record review and data collection from ICU admission		X	
Physical exam of arms or legs, and for sexual maturity rating ^a		X	X
Administration of enoxaparin ^b		X	
Measure Anti-Xa activity ^c		X	
Ultrasound ^d			X
Bleeding assessment ^e		X	X
Assess for AEs ^{e,f}	X	X	X
CBC with differential ^g		X	
Renal function tests (BUN, creatinine) ^g		X	
Serum aminotransferases ^g		X	
Stool occult bleed ^h		X	
Blood collection for correlatives		X ⁱ	X
Urine collection for correlatives		X ⁱ	X

a: At time of enrollment for physical exam of arms or legs (if patient has a CVC in the internal jugular vein, only arms need to be examined; if the CVC is inserted in the femoral vein, only legs need to be examined), and at any time during the admission for the sexual maturity rating.

b: 1st dose <24 hours after insertion of the CVC, then every 12±2 hours until CVC removal. Only for subjects randomized to the treatment arm.

c: Anti-Xa activity will be measured 4-6 hours after the 3rd dose, then every 3rd dose until target is achieved. After target achieved, measurement is weekly.

d: Within 24 hours of removal of the CVC, or earlier upon discharge from the ICU, radiologic diagnosis of CADVT, start of therapeutic anticoagulation, clinically relevant bleed develops, HIT is diagnosed, or 28 days after insertion of the CVC

e: Daily.

f: Starting from time permission form is signed until 30 hours after the last dose of enoxaparin in the trial.

g: Within 48 hours of enrollment and at least weekly ± 2 days, thereafter.

h: If clinically indicated as determined by the site PI.

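### The Aim 2 decision uses ETP at D2, before any anti-Xa-driven dose change can act, so it tests the starting regimen and not the titrated strategy that the aim names

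*Combined protocol and SAP*

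**What the plan says.** The objectives section gives Aim 2 as "To evaluate the effect of an anti-Xa activity-directed prophylactic strategy on thrombin generation in critically ill children". Its hypothesis is that the "standard prophylactic dose of enoxaparin adjusted by anti-Xa activity reduces thrombin generation to <700 nM·min, as measured by ETP".

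Statistical Considerations sets the Aim 2 decision on a posterior probability that ETP with enoxaparin is below 700 nM·min, computed "for difference of means of ETP at D2 after 100 subjects complete the trial". The reason given for the time point is "We chose D2 because anticoagulation should be achieved as soon as possible". A posterior probability of at least 0.60 "will be used to decide on the dose for a phase 3 trial". The same section says that, if Aim 1 falls short, Aim 2 will show whether a higher dose is appropriate.

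Correlative Samples places D2 24±6 h after D1, "or together with the blood draw for the anti-Xa activity for subjects in the treatment arm". The flow chart fixes the anti-Xa schedule in footnote c: "Anti-Xa activity will be measured 4-6 hours after the 3rd dose, then every 3rd dose until target is achieved". The dose worksheet in Appendix II treats doses 1 to 3 as the initial dose. ETP across D1-D4 is modelled as a secondary analysis, with treatment arm as the main predictor.

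**The concern.** The aim and hypothesis are about a strategy: start, measure anti-Xa, adjust. If the decisive sample is taken before an adjustment can happen, a trial with a fixed dose and no titration would produce the same D2 data. The result would still be reported as the effect of anti-Xa-directed dosing and would inform the phase 3 dose. Suppose the starting dose left ETP high but titration corrected it by day 4. The rule would record failure, although the strategy had worked as intended.

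A second problem concerns what D2 measures within the enoxaparin arm. One permitted timing is tied to D1 and the other to a peak anti-Xa sample. ETP at D2 may then depend partly on which option a site used.

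**Working it through.** The documents give no sample size, power or operating characteristic for Aim 2, so there is no stated figure to reproduce. The check is arithmetic on the time windows.

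**Inputs**
- Dose interval 12±2 h (Treatment Regimen).
- First anti-Xa level 4-6 h after dose 3 (flow chart, footnote c). The wording under Titration dose could be read as a level after each of the first three doses, but the flow chart and the Appendix II worksheet settle it as after dose 3.
- D1 before the first dose in the treatment arm (flow chart, footnote i). Correlative Samples attaches that condition to the control arm, which receives no enoxaparin; the two places need reconciling.
- D2 at 18-30 h after D1, or with the anti-Xa draw.

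**Step 1: when titration can first act.** Taking dose 1 as time 0, dose k falls at (k - 1) × interval, and each level falls 4-6 h after its dose.

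| Interval | Dose 3 | First anti-Xa level | Dose 4 | Second anti-Xa level (after dose 6) |
|---|---|---|---|---|
| 10 h | 20 h | 24-26 h | 30 h | 54-56 h |
| 12 h | 24 h | 28-30 h | 36 h | 64-66 h |
| 14 h | 28 h | 32-34 h | 42 h | 74-76 h |

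Dose 4 is the first dose an anti-Xa result can change, at 30-42 h.

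**Step 2: where D2 falls.** D1 precedes dose 1, so D2 on the 24±6 h option is at most 30 h after dose 1, and earlier by however long D1 preceded dose 1. The latest D2 (30 h) is no later than the earliest dose 4 (30 h). A D2 drawn with the first anti-Xa level also precedes dose 4.

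A simulation of 1,000,000 schedules, uniform within each window, tried maximum D1-to-dose-1 gaps of 0, 4, 12 and 23 h (the documents give no gap). On the 24±6 h option:
- D2 followed dose 4 in none of the schedules, at any gap.
- D2 followed the first anti-Xa level in about 11% (no gap) down to 0.6% (gap up to 23 h).
- D2 preceded dose 3 in about 50% (no gap) up to 93% (gap up to 23 h).

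**Step 3: mixed post-dose phases.** The fraction of the level at time t that remains at 12 h is 2^(-(12 - t)/half-life). The Excretion section gives half-lives of 4.5 to about 7 h.

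| Half-life | t = 4 h | t = 5 h | t = 6 h |
|---|---|---|---|
| 4.5 h | 0.29 | 0.34 | 0.40 |
| 7 h | 0.45 | 0.50 | 0.55 |

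A near-trough draw and a 4-6 h draw therefore differ about 2- to 3-fold in anti-Xa. If D1 is taken just before dose 1, 24 h later is the nominal time of dose 3, which is near trough. If D1 precedes dose 1 by 8 h, the same draw is 24 - 8 = 16 h after dose 1, or 4 h after dose 2, which is near peak. The unstated gap decides which applies.

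**Step 4: what D3 would offer.** D3 is 4 days (96 h) after insertion and dose 1 is 0-24 h after insertion, so D3 is 72-96 h after dose 1. That follows dose 4 in every simulated schedule and follows the second anti-Xa level in more than 99.9%.

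The investigators' earlier cohorts had a mean catheterisation of 6 days (SD 5). The share still catheterised at day 4 would be 57% under a gamma shape, 58% under a lognormal, and exp(-4/6) = 51% under an exponential with mean 6. These shapes are assumed. Of about 50 children on enoxaparin, that is about 26-29.

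**The case against.** D2 has a rationale. The background says nearly all catheter-associated thrombosis has developed by day 4, and its adult ETP benchmark is taken 24 h after the first dose. Early ETP is therefore the relevant window for early prophylaxis. A titrated strategy also includes its starting dose, and a child whose first level is 0.20-0.50 IU/mL keeps that dose. For other children, short of a hold above 1.00 IU/mL, each step is only 10-20%. All of this stands. It supports studying ETP at D2, but it does not turn D2 into a test of adjusted dosing.

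Three stronger readings are tempting and not supported:
- A reader might infer that every D2 is drawn at or before the first anti-Xa level. With 10 h intervals that level is at 24-26 h and D2 may be at 30 h. What holds is that D2 precedes the first dose anti-Xa can change.
- A reader might infer that the trial cannot answer Aim 2. The planned D1-D4 mixed model and the ETP/anti-Xa models can use samples taken after titration. They lack a decision rule.
- A reader might infer that D3 must replace D2. D3 is not tied to dose time, comes when most thrombosis has already formed, and covers a selected group with longer catheterisation. Enoxaparin ends at catheter removal, so an on-treatment D3 does not exist for the others.

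**Conclusion.** The mismatch is real. Within the protocol's windows, no D2 sample follows an anti-Xa-adjusted dose, so the Aim 2 decision concerns the starting regimen. That regimen is already modified for age, obesity and renal function; what it lacks is adjustment by anti-Xa.

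This rests on three conditions: D1 is pre-dose in the enoxaparin arm, dosing stays within 12±2 h, and the anti-Xa draw that D2 may accompany is the first one. The text does not name the draw, but the second level, nominally at 64-66 h, would contradict the 24±6 h target.

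The effect of the mismatch on ETP is not quantified; absence of titration at D2 is a timing fact. The 2- to 3-fold difference in drug level is a separate matter of draw timing. It relies on mainly adult half-lives and on the unknown gap between D1 and dose 1. How far ETP would move with it is uncertain: the protocol's own correlations of ETP with anti-Xa (-0.59 and -0.51) come from 9 samples in 4 children on heparin.

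**What to change.** 1. Restate the D2 hypothesis, decision rule and conclusion as applying to the starting regimen, and do not report D2 as the effect of the anti-Xa-directed strategy.
2. In the enoxaparin arm, always draw D2 with the first anti-Xa level, 4-6 h after dose 3. Record time since last dose for every ETP sample.
3. Report the treatment effect on ETP at D3 from the already planned D1-D4 mixed model as the read-out for the titrated strategy, stating that it applies to children still catheterised at day 4.

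Whether D3 should replace D2 as the decisive time point is a trade-off for the sponsor.

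The cost is wording in the protocol, analysis plan and laboratory manual, plus one recorded time per sample; D3 is already collected. D2 in the enoxaparin arm falls slightly later, nominally 28-30 h after dose 1. The D3 estimate is less precise and comes from a selected group.

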APPENDIX I

Infants and Children 0 to 2 Years of Age Weight-for-length 95th Percentiles, 45 cm to 110 cm

Length (cm)	Male (kg)	Female (kg)
45	2.85	2.87
46	3.04	3.07
47	3.23	3.26
48	3.43	3.47
49	3.64	3.68
50	3.87	3.91

Length (cm)	Male (kg)	Female (kg)
81	12.23	11.98
82	12.45	12.23
83	12.69	12.49
84	12.94	12.76
85	13.20	13.04
86	13.47	13.33
87	13.75	13.62
88	14.02	13.92
89	14.30	14.21
90	14.57	14.50
91	14.83	14.79
92	15.10	15.08
93	15.37	15.37
94	15.64	15.67
95	15.91	15.96
96	16.19	16.26
97	16.48	16.57
98	16.78	16.88
99	17.09	17.19
100	17.41	17.52
101	17.74	17.86
102	18.09	18.21
103	18.44	18.58
104	18.80	18.96
105	19.17	19.34
106	19.55	19.75
107	19.95	20.16
108	20.35	20.60
109	20.76	21.04
110	21.18	21.50

51	4.11	4.16
52	4.36	4.42
53	4.64	4.70
54	4.94	5.00
55	5.26	5.31
56	5.58	5.62
57	5.91	5.93
58	6.25	6.25
59	6.57	6.55
60	6.90	6.86
61	7.20	7.15
62	7.50	7.44
63	7.79	7.72
64	8.07	8.00
65	8.35	8.26
66	8.62	8.53
67	8.89	8.78
68	9.15	9.03
69	9.41	9.28
70	9.68	9.52
71	9.94	9.75
72	10.19	9.99
73	10.45	10.21
74	10.69	10.44
75	10.93	10.66
76	11.16	10.87
77	11.39	11.08
78	11.60	11.29
79	11.81	11.51
80	12.02	11.74

Adopted from: *Centers for Disease Control and Prevention, National Center for Health Statistics, 2010*

(http://www.cdc.gov/growthcharts/html_charts/wtleninf.htm)

Male and Female 2-20 Years Old Data Table of 95th Percentile BMI Value for Age

Body Mass Index, or BMI, is calculated
using the following formula:

$$\text{BMI} = \text{Weight (in kilograms)} / \text{Height (in meters)}^2$$

Age	Male (BMI)	Female (BMI)
2	19.34	19.11
2.5	18.67	18.58
3	18.24	18.25
3.5	17.97	18.08
4	17.84	18.03
4.5	17.83	18.09
5	17.94	18.26
5.5	18.14	18.51
6	18.41	18.84
6.5	18.76	19.23
7	19.15	19.68
7.5	19.59	20.17
8	20.07	20.70
8.5	20.57	21.25
9	21.09	21.82
9.5	21.62	22.40
10	22.15	22.98
10.5	22.69	23.57
11	23.21	24.14

Adopted from: Centers for Disease Control and
Prevention, National Center for Health Statistics, 2001
(http://www.cdc.gov/growthcharts/html_charts/bmiagerev.htm)

11.5	23.73	24.71
12	24.23	25.26
Age	Male (BMI)	Female (BMI)
12.5	24.71	25.79
13	25.18	26.30
13.5	25.62	26.79
14	26.05	27.26
14.5	26.45	27.70
15	26.84	28.12
15.5	27.21	28.53
16	27.56	28.91
16.5	27.91	29.28
17	28.26	29.63
17.5	28.60	29.98
18	28.96	30.33
18.5	29.33	30.67
19	29.73	31.03
19.5	30.16	31.40
20	30.59	31.76

APPENDIX II

DOSE CALCULATION WORKSHEET

Subject #:	Subject Name:	Subject MRN:
Age:	Weight (kg):	Height (cm):
Date:	Dose Sequence: (e.g. 1-3, 4-6, etc)	BMI (only applicable for age 2-18)
	kg	cm
		kg/m ²

SECTION I					
Instructions for initial dose (#1-3), otherwise skip to Section II					
1. Using the table below, select dose for patient based on patient's age: _____ mg/kg					
Age	Drug	Dose/Potency	Dose Frequency	Route	Regimen/ Treatment Period
Children ≤2 months	Enoxaparin	0.75 mg/kg	Every 12 hours	Subcutaneous	Until CVC is removed
Children > 2 months	Enoxaparin	0.5 mg/kg (maximum of 30 mg)	Every 12 hours	Subcutaneous	Until CVC is removed
2. Evaluate patient's characteristics for dose modification.					
a. For subject between the ages of 0 to 2 years old, does the weight for the corresponding height exceed the 95th percentiles weight provided in Appendix II? _____ Yes _____ No					
• If yes, double the dose due to obesity					
b. For subject between the age of 2 to 18 years old, does the BMI for the corresponding age exceed the 95th percentiles BMI provided in Appendix III? _____ Yes _____ No					
• BMI = (Weight (in kilograms)/Height (in meters ²))					
_____ kg/m ² = (_____ kg / (_____ m) ²)					
• If yes, dose is doubled due to obesity.					
3. Based on patient's age and obesity status, input dose into Section II under "mg/kg Dose Selected"					

SECTION II		
mg/kg Dose Selected	Serum Creatinine	Anti-Xa Activity
mg/kg	mg/dL	IU/mL
Step 1: Renal function		

 Determine the subject's k constant: 
 k is 0.33 in premature infants through the first year of life k is 0.43 for term infants through the first year of life k is 0.55 in boys age 2-12 years old and girls of any age k is 0.70 in adolescent boys over the age of 12 Calculate Glomerular Filtration Rate using Schwartz Equation: $GFR = k * Height (cm) / SCr (mg/dL)$ 		
_____ mL/min/1.73m ² = (_____ x _____ cm) / (_____ mg/dL)		
Using the Schwartz equation, is GFR less than 75 mL/min/1.73 m ² ? _____ Yes _____ No		
• If yes, halved the dose selected from Section I due to renal insufficiency.		
What is the current dose based on renal function? _____ mg/kg		
Step 2: Dose Calculation (1st Dose)		
Take the dose (mg/kg) determined in step 1 and multiply it by the patient's weight (kg)		
_____ mg (maximum of 30mg) = _____ mg/kg (dose) x _____ kg (weight)		
Step 3: Dose Titration (Subsequent Doses)		
Select the appropriate titration factor corresponding to the anti-Xa activity.		
Anti-Xa Activity	Enoxaparin Dose Titration	Titration Factor (TF)
<0.1 IU/mL	Increase dose by 20%	1.2
0.1-0.19 IU/mL	Increase dose by 10%	1.1
0.2-0.5 IU/mL	Keep same dosage	1
0.51-1 IU/mL	Decrease dose by 10%	0.9
>1 IU/mL	Hold all doses until anti-Xa is 0.3, IU/mL, then decrease dose by 20%	0.8
Next Anti-Xa Activity Check		
After 3 rd dose		
Check in 1 week		
After 3 rd dose		
Before next dose and every 12 hours, until anti-Xa <0.3 IU/mL		
Subsequent Dose		
_____ mg (maximum of 30mg) = _____ mg (previous dose) x _____ (TF)		
Step 4: Volume Calculation		
Take the dose (mg) calculated in Step 2 or Step 3 and divide it by 20 mg/mL concentration for doses <10mg. Use 100mg/mL concentration for doses ≥10mg to obtain the volume that needs to be dispensed in a Vanish Point or another suitable syringe.		
_____ mL = _____ mg / _____ mg/mL (****Round the dose volume to the nearest hundredth****)		
Step 5: Dispensing		
Dispensed _____ mL (step 4) of enoxaparin in a Vanish Point or other suitable syringe. Dose is stable for 24 hours. Discard any unused drug.		

Pharmacist's or Designee's Signature/Print Name: _____ Date: _____

